6.4.2 Quality assurance of surgery

Using the per protocol set, the null hypothesis of true equality of quality of surgery being achieved with LAO and OO will be tested for each measure in turn. As the per protocol set is being employed here, conclusions will need to be cautious, and only simple tests will be used: e.g. t-tests for normally distributed continuous measures, Mann-Whitney U tests for markedly non-normal continuous measures, and chi-square tests for binary measures.

6.4.3 pStage based on resection

Staging based on the resection will be categorised according to the American Joint Committee on Cancer 8th Edition.(9)

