2.7 Sample size and justification

The theoretical advantage of LAO compared to OO for patients is improved short-term recovery with the long-term survival benefit of surgery maintained. Consequently, the primary endpoint is the QLQ C30 Physical Function sub-scale measured at three and six-weeks post-surgery and three months post-randomisation.

For simplicity, and to indicate the minimum statistical power that will be achieved for the comparison of recovery, we consider just the six-week assessment of physical function. The planned analysis, based on the three-week, six-week, and three-month assessments of patient-reported physical function (primary outcome), and the baseline assessment as a covariate, is likely to have greater power than indicated here.

We are assuming that having adjusted analyses for centre, there will be no further need to accommodate clustering of outcomes by surgeon. In fact, as a team of surgeons is involved in each case (in decision-making, in-hospital care, and often in theatre), it would be difficult to do in practice.

A recent review of patient reported outcomes has indicated that the minimum clinically important difference on the QLQ-C30 Physical Function Scale is 0.4 standard deviations (1). Allowance for 5% of patients allocated to LAO undergoing OO, and 10% of patients in each group being found during surgery to have more extensive disease, can be achieved by reducing the effect size to be detected to 0.34 standard deviations. In this situation 182 patients in each group (364 patients in total) will allow a true treatment effect (LAO versus OO) of 0.4 standard deviations to be detected with 90% power at the 5% significance level, when up to 15% of patients are not able to follow their allocated procedure.

Further allowing for up to 10% missing outcome data, e.g. due to the patient being too sick, increases the target sample size to $364/0.9 = 406$ patients in total. Hence our sample size target for the definitive ROMIO trial is 203 patients allocated to LAO and 203 patients allocated to OO.

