2.10.2 Secondary outcomes

Secondary outcomes will assess the efficacy of the two approaches (morbidity and safety) and establish oncological markers of quality assurance of surgery which are surrogate markers of long-term survival (detailed histopathology and quality assurance of the radicality of surgery). Secondary outcomes will include:

1. All-cause short and long-term complications
2. Impact of complications up to hospital discharge will be categorised using the Clavien-Dindo System(2).
3. Spirometry measures of forced expiratory volume in one second (FEV₁) and forced vital capacity (FVC)
4. Success of blinding during the first six days post-surgery, using the Bang Blinding Index(3).
5. Generic and disease specific HRQL measures EORTC QLQ-C30(4), and QLQ-OES18(5), multidimensional fatigue inventory (MFI-20)(6), EuroQoL EQ-5D-5L(7) from which we will calculate quality adjusted life years (QALYs).
6. Quality assurance of surgery with histopathological and surgical measures
7. Overall and recurrence-free survival to two years
8. Length of hospital stay, defined as length of primary hospital stage plus readmission within 30 days (and length of primary hospital stay plus length of hospital stay if discharged to community hospital)
9. Further measures of NHS resource use and costs.

The assessment points are pre-surgery, post-surgery at three days, six days, three weeks, and six weeks, and post-randomisation at three, six, nine, twelve, eighteen and 24 months.

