3. GENERAL ANALYSIS CONSIDERATIONS

3.1 Analysis populations

Each of the following will include participants of the feasibility and main trials, according to the availability of data.

The primary effectiveness analysis will include data from the **“full analysis set”**; all randomised participants **in the groups to which they were allocated** (i.e. according to the intention-to-treat principle) who provide at least one of the three post-treatment assessments of physical function contributing to the primary outcome.

The **“safety set”** will include all randomised participants for whom there was an attempt to complete a study procedure (OO or LAO). This does not include patients for whom curative surgery did not proceed (e.g. due to the discovery of more advanced disease). The safety set does include participants who underwent a study procedure which was not that allocated, and participants who needed to convert from LAO to OO due to clinical reasons. This is the analysis population that will be used in the reporting of complications and adverse events. The groups to be compared will be defined by the study procedure **first initiated**, e.g. participants will be retained in the LAO group, even if they subsequently needed to convert to OO.

The **“per protocol set”** will include all randomised participants, **in their allocated groups**, for whom the allocated surgery was completed. Analyses of blinding, and surgical quality will use data from these participants.

Within the above three sets, about 120 feasibility phase patients, allocated to OO or LAO and with the necessary data, will be distinguished from those patients allocated to OO and LAO in the main study. In general, estimates of effectiveness will be stratified by feasibility and main study, and presented with a third pooled estimate using data from the two study phases.

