5.5 Fidelity to allocated surgery

Surgeons are completing check-lists for, and photographing key aspects of each procedure, to assess whether they are abiding by the listed mandatory and prohibited actions for OO, and for LAO. The number of procedures for which fidelity was maintained will be reported by study arm for patients in the per protocol set, and the nature of the deviation presented by study group for other patients.

Conversions from allocated surgery to another approach, and cases where the allocated surgery could not be completed, will be reported in the CONSORT flow chart (these patients are not part of the per protocol set) and reasons noted in the text.

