For the per protocol set, summary statistics for the histopathological and surgical measures of quality will be presented for each of the LAO and OO groups, including length of oesophagus, total count of malignant ‘positive’ nodes, total count of all nodes, carcinoma positive circumferential resection margins, carcinoma positive proximal and distal resection margins, and pT stage.

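### Nodes, margins and stage are compared only in the per protocol set, which excludes patients converted from LAO to OO, a loss the plan foresees in one arm only

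*SAP*

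**What the plan says.** Section 3.1 defines the per protocol set as randomised participants, in their allocated groups, "for whom the allocated surgery was completed. Analyses of blinding, and surgical quality will use data from these participants". Section 6.2 uses it for description: "For the per protocol set, summary statistics for the histopathological and surgical measures of quality will be presented". Section 6.4.2 uses it for testing: "Using the per protocol set, the null hypothesis of true equality of quality of surgery being achieved with LAO and OO will be tested". That section adds that, because of this choice of set, conclusions should be cautious and the tests simple.

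Section 5.5 says that conversions, and operations that could not be completed as allocated, "will be reported in the CONSORT flow chart (these patients are not part of the per protocol set) and reasons noted in the text".

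The sample size section (2.7) expects losses of two kinds: "Allowance for 5% of patients allocated to LAO undergoing OO, and 10% of patients in each group" found at operation to have more extensive disease. It gives no rate for OO patients having LAO.

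Section 2.10.2 describes the histopathology as "oncological markers of quality assurance of surgery which are surrogate markers of long-term survival".

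For complications the plan uses a different rule. The safety set in Section 3.1 groups patients by the procedure first started, so a patient converted from LAO stays in LAO.

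**The concern.** Whether the allocated operation was completed is known only after randomisation and may depend on how difficult the case was. A patient converted from LAO to open access can still have a resection, with node counts and margins, but leaves the comparison. An OO operation of equal difficulty that is completed as allocated stays in. If converted cases tend to give worse specimens, LAO is judged on a more favourable selection of its patients than OO is.

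Section 7 puts Table 4, which holds these measures, in the first paper, after the three-month assessments. The 24-month survival analysis follows in a later paper. Apart from 30-day and 90-day mortality, the histopathology is the oncological comparison that readers see first. Table 4 lists nodes, margins and pStage beside hospital stay, lung function and pain, which Sections 6.4.5 to 6.4.7 analyse in the full analysis set. It does not say that the sets differ. Section 6.6 changes the analysis set only for six-day pain, so no planned result shows what the exclusion does to surgical quality.

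**Working it through.** **1. The plan's own figure.** From Section 2.7: effect 0.4 SD, 15% not following allocation, 90% power, 5% significance (taken as two-sided).
- Diluted effect: 0.4 × 0.85 = 0.34 SD.
- Patients per group: 2 × (1.960 + 1.282)² / 0.34² = 181.8, so 182.
- Allowing for 10% missing: 182 / 0.9 = 202.2, so 203 per group and 406 in total.

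This agrees with the plan. The SAP gives no figure for the surgical-quality comparison, so the rest uses its rates plus stated assumptions.

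**2. Who is kept.** Take the 10% with more extensive disease as not completing the operation in either arm, and the 5% as separate patients (together they make the plan's 15%). Take no OO patients as departing from allocation, since no rate is given.
- OO per protocol: 203 × 0.90 = 182.7, about 183.
- LAO per protocol: 203 × 0.85 = 172.6, about 173.
- LAO patients dropped beyond the loss common to both arms: 203 × 0.05 = 10.15, about 10.
- Share of resected LAO patients dropped: 0.05 / 0.90 = 5.6%.

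**3. Size of the shift.** For a binary measure such as a positive margin, shift = share dropped × (rate in converted − rate in unconverted). Assume 20% in unconverted LAO. The false-positive rate below takes the two arms as truly equal over all resected patients, so the OO rate is 20% plus the shift. Then SE = √[0.20 × 0.80 / 172.55 + p(1 − p) / 182.7], with p the OO rate, and the rate is the two-sided normal tail beyond 1.96 when the mean of Z is shift / SE.

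| Assumed rate in converted | Rate over all LAO resections | Rate the plan would show | Shift (points) | SE (points) | False-positive rate |
|---|---|---|---|---|---|
| 20% | 20.0% | 20% | 0 | 4.25 | 5.0% |
| 30% | 20.6% | 20% | 0.6 | 4.27 | 5.2% |
| 40% | 21.1% | 20% | 1.1 | 4.29 | 5.8% |
| 50% | 21.7% | 20% | 1.7 | 4.31 | 6.7% |
| 60% | 22.2% | 20% | 2.2 | 4.33 | 8.1% |

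For a continuous measure, an assumed 0.5 SD deficit in converted patients shifts the comparison by 0.0556 × 0.5 = 0.028 SD, with a false-positive rate of 5.8%.

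**4. Sensitivity to the conversion rate.** If 10% of LAO patients were converted (an assumption with no basis in the SAP), the share dropped is 0.10 / 0.90 = 11.1%. The shift for converted rates of 30-60% doubles to 1.1 to 4.4 points.

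**The case against.** **The size is small and the direction is assumed.** This stands. At the planned 5% the shift is well inside one standard error, and nothing in the SAP shows that converted cases have worse specimens. Section 2.7 also does not say whether its 5% means conversion during surgery, crossover beforehand, or both. Both fall outside the set, but crossovers by choice need not be harder cases.

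**OO loses patients too.** This also stands. The rule removes OO patients whose surgery was not completed or who had another procedure, and Section 5.4 does not confine patient choice to one arm. A reader might infer that OO is judged on every resection. The documents do not say so. What they show is a planning allowance for one direction only, and Section 3.1 mentions conversion only from LAO to OO.

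**The per protocol set answers a fair question and the plan is open about it.** Section 6.4.2 asks what each technique achieves. A converted specimen was finished by open access, so keeping it in LAO can dilute a real difference. That is a reason to show the per protocol result, but not to show it alone. Cautious wording does not tell a reader which way, or how far, the result has moved.

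**Survival is analysed as allocated.** Section 6.4.8 uses the full analysis set, so the histopathology does not carry the oncological case alone. It is, however, reported first.

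**Fidelity.** Because Section 5.5 says "The number of procedures for which fidelity was maintained will be reported by study arm for patients in the per protocol set", a reader might infer that failures to deliver LAO are hidden. They are not. The same sentence continues "and the nature of the deviation presented by study group for other patients", and conversions appear in the CONSORT chart with reasons.

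**Conclusion.** The point holds for the surgical-quality measures. They are described and tested only in a set defined after randomisation, from which the plan itself expects to lose about 10 more LAO than OO patients (about 173 against 183 kept of 203 each). No analysis that retains them is planned, although the safety set already has a rule that keeps converted patients in LAO.

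The lean towards LAO is conditional. It is 0.6 to 2.2 points on a binary measure at 5% conversion, if 20% of unconverted and 30-60% of converted cases are adverse. It is larger if conversions are more frequent and zero if converted cases do not differ. The documents do not support calling the comparison biased towards LAO as a matter of fact. The change is worth making because the plan treats these measures as surrogates for survival and the remedy is cheap.

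**What to change.** - **Sections 3.1, 6.2 and 6.4.2:** analyse nodes, margins and pStage in all randomised patients with a resection specimen, in their allocated groups, keeping conversions and crossovers. Present the per protocol result beside it.
- **Section 6.4.3:** state the same set for pStage, since that section names none.
- **Table 4:** label the analysis set for the node, margin and pStage rows.
- **Optional, Section 5.5:** also give the fidelity count over all procedures started. This is a matter of presentation only.

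The set of patients with a specimen is itself fixed after randomisation, because those without a resection are absent. It does, however, avoid removing patients for having been converted, and the plan expects the loss to more extensive disease to be the same 10% in each arm.

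The cost is SAP wording and a second set of simple tests. It should need no new data collection, provided specimens from converted patients were reported like the others. The price is some dilution of the technique comparison by converted cases, and LAO figures that may look slightly less favourable.

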6.4.4 Surgical complications during hospital stay

Using the safety set, the null hypothesis of true equality in the proportion of patients experiencing one or more episodes of each of the key complications (oesophagoenteric leak, conduit failure, chyle leak, pneumonia, GI bleeding requiring intervention) will be tested using a chi-square test.

For each patient the most severe impact of any complications during their initial hospital stay will be categorised using the Clavien-Dindo system(2), patients in the LAO and OO groups being compared using ordered logistic regression.

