6.4.7 Length of hospital stay

Using the full analysis set, total and post-surgical inpatient stay will be compared between LAO and OO groups. Medians and first and third quartiles will be presented. The evidence against the null hypothesis of no difference in hospital stay between OO and LAO groups will be quantified using the Mann-Whitney U test.

6.4.8 Overall and recurrence-free survival to two years.

A Kaplan-Meier plot will present survival over time in the OO and LAO groups. Kaplan-Meier estimates of survival, with 95% confidence intervals will be presented for survival in each of the OO and LAO groups at the following time points: 30 days, 90 days, 24 months.

Using the full analysis set, the hazard ratio comparing those allocated to LAO to those allocated to OO in terms of all-cause mortality, and recurrence-free survival will be estimated using proportional hazards models with time to event as the outcome measure and covariates: allocated surgery, dummy variables distinguishing the centres, and a dummy variable distinguishing those patients who underwent neoadjuvant treatment, and those who did not. Marked evidence against the proportional hazards assumption will be investigated in a test based on Schoenfeld residuals(10). Estimated hazard ratios will be presented with 95% confidence intervals.

This analysis is aimed at ruling out a large difference in survival between LAO and OO, as the benefit of LAO is expected to be limited to faster recovery in the initial months post-surgery. Our equivalence bound is a 7% difference in mortality risk, such that the 95% confidence interval for the risk difference at 24 months post-randomisation is entirely within the range -7% to +7%.

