Pneumonia / chest infection			
Delayed gastric emptying			
GI bleeding requiring intervention or transfusion			
Acute abdominal wall dehiscence/hernia			
Further intervention, n (%)			
Reoperation during index hospitalisation			
Return to ITU/HDU during index hospitalisation			
Within three months of randomisation			

Table 4. Peri- and post-surgical measures

	OO (n=)	LAO (n=)	p-value
30-day post-operative mortality, n (%)			
90-day post-operative mortality, n (%)			
Median total hospital stay in days (Q1, Q3) ¹			
Median post-surgical hospital stay in days (Q1, Q3) ¹			
Median total lymph nodes retrieved (Q1, Q3) ¹			
Median lymph nodes with tumour (Q1, Q3) ¹			
Resection margins, n (%)²			
R0			
R1			
R2			
pStage, n (%)²			
0			
I or II			
III			
IV			
No residual tumour or lymph-node metastasis			
Median FEV₁, as a percentage of pre-surgery (Q1 Q3), n			
Three days post-surgery ¹			
Six days post-surgery ¹			
Median FVC, as a percentage of pre-surgery (Q1 Q3), n			
Three days post-surgery ¹			
Six days post-surgery ¹			
Median pain (Q1, Q3), n; 0 is no pain, 100 is worst possible pain.			
Three days post-surgery ¹			
Six days post-surgery ¹			

1. p-value based on Mann-Whitney U statistic. Note that Q1 and Q3 are the first and third quartiles

2. p-value based on ordered logistic regression

Supplementary Table 1. Post-surgery treatment complications in those undergoing their allocated surgery [specific complications will be detailed if they occur in one or more patients – those listed here are examples only]

	OO (n=)	LAO (n=)
Pulmonary complications, n (%)		
Respiratory failure requiring intubation		
Acute respiratory distress syndrome		
Cardiac complications, n (%)		
Dysrhythmia atrial requiring treatment		
Dysrhythmia ventricular requiring treatment		
Urological complications, n (%)		
Acute renal insufficiency		
Gastrointestinal complications, n (%)		
Anastomotic stricture requiring endoscopic intervention		
Thromboembolic complications, n (%)		
Pulmonary embolism		
Neurological / psychiatric complications, n (%)		
Other neurological injury		
Post-operative infections, n (%)		
Wound infection requiring opening wound or antibiotics		
Post-operative wound / diaphragm complications, n (%)		
Acute abdominal wall dehiscence / hernia		
Other post-operative complications, n (%)		
Multiple organ dysfunction syndrome		

Supplementary Table 2. Cohort stratified and pre-specified subgroup analyses

	OO (n=)	LAO (n=)
Main study cohort		

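### Surgical quality, key complications and early mortality are compared by p-value alone, with no between-arm estimate or 95% confidence interval to show how much excess risk with LAO remains possible

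*SAP*

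**What the plan says.** **Surgical quality.** In SAP section 6.4.2, which works in the per protocol population, the rule is that "the null hypothesis of true equality of quality of surgery being achieved with LAO and OO will be tested for each measure in turn". The tests are t, Mann-Whitney or chi-square according to the type of measure. The section adds that, because of the population used, "conclusions will need to be cautious, and only simple tests will be used".

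**Complications.** Section 6.4.4 uses the safety set. Its hypothesis is "the null hypothesis of true equality in the proportion of patients experiencing one or more episodes of each of the key complications". Each such complication "will be tested using a chi-square test". The section compares Clavien-Dindo grades by ordered logistic regression without asking for an odds ratio or interval.

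**Tables.** In section 8, Tables 3 and 4 have three columns: OO, LAO and p-value. Resection margins (R0/R1/R2) and pStage carry the footnote "p-value based on ordered logistic regression". For 30- and 90-day mortality Table 4 has a p-value cell, but no test is named.

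**Contrast within the plan.** A 95% interval is specified for the primary treatment effect (6.3), the subgroup effects (6.5) and the hazard ratios (6.4.8). For 24-month mortality, 6.4.8 sets an equivalence bound, met if "the 95% confidence interval for the risk difference at 24 months post-randomisation is entirely within the range -7% to +7" per cent. At 30 and 90 days, 6.4.8 gives Kaplan-Meier intervals for each arm, not for the difference.

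**The concern.** Section 2.7 describes the expected advantage of LAO as "improved short-term recovery with the long-term survival benefit of surgery maintained", and section 2.10.2 calls the surgical quality measures "oncological markers of quality assurance of surgery which are surrogate markers of long-term survival". For these measures and for complications, what a reader most needs to know is whether LAO could be materially worse, and by how much. A p-value against equality does not answer that. A large p-value may come from a small difference measured precisely or from a sizeable difference measured poorly, and the tables as laid out do not separate the two.

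Timing adds weight. Under section 7, Tables 3 and 4 belong to the first paper (late 2019), and the survival analysis follows in autumn 2021. For about two years these p-values are the only planned between-arm inference on surgical safety and radicality.

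**Working it through.** **1. The plan's own sample size.** With 0.34 SD, two-sided 5% and 90% power, n per arm = 2(1.960 + 1.282)²/0.34² = 181.8, so 182, as section 2.7 states. The SAP gives no event rate, power or margin for complications or surgical quality, so the base rates below are assumptions.

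**2. Numbers per arm.** Section 2.7 targets 203 per arm and expects 10% to have more extensive disease at surgery: 203 × 0.9 = 182.7, about 183 in the safety set. If the 5% of LAO patients who receive OO are also removed, the per protocol LAO arm is 203 × 0.85 = 172.6, about 173.

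**3. Power of the two-sided 5% chi-square test, 183 per arm.** With p₀ the OO rate, p₁ = p₀ + d the LAO rate, p̄ their mean and q = 1 − p:

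power = Φ{[d − 1.96√(2p̄q̄/n)] / √[(p₀q₀ + p₁q₁)/n]}

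For 10% v 15%: √(2 × 0.125 × 0.875/183) = 0.03457 and √[(0.09 + 0.1275)/183] = 0.03448, so power = Φ[(0.05 − 0.06776)/0.03448] = Φ(−0.515) = 0.30.

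The last column is the approximate 95% half-width for a risk difference, 1.96√(2p₀q₀/183).

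| Assumed OO rate | +5 points | +7 points | +10 points | Half-width (points) |
|---|---|---|---|---|
| 5% | 44% | 67% | 89% | 4.5 |
| 10% | 30% | 50% | 77% | 6.1 |
| 15% | 24% | 41% | 67% | 7.3 |
| 20% | 21% | 35% | 60% | 8.2 |
| 30% | 17% | 29% | 52% | 9.4 |

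Exact power, summing binomial probabilities over all 2×2 tables, differs by at most about 1.3 points (10% v 15%: 0.308; 10% v 17%: 0.508).

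A 5-point rise is therefore missed more often than not at every rate shown. A 7-point rise is missed more often than not from about 15% upwards, is about even at 10%, and is usually detected at 5%. Ten-point rises from 5% to 20% are detected more often than not; from 30% the chance is about even.

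**4. Sensitivity to the numbers.** With all 203 per arm, power for 5 points runs from 48% (base rate 5%) down to 19% (30%), and for 7 points it is 44% at a base rate of 15%. Per protocol sizes of 183 v 172 give 30% for 10% v 15% and 40% for 15% v 22%. The pattern is unchanged.

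**5. What the table would hide.** Suppose leaks are 18/183 (9.8%) on OO and 28/183 (15.3%) on LAO.

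- Difference: 5.46 points.
- Test: pooled rate 46/366 = 12.57%, standard error √(0.1257 × 0.8743 × 2/183) = 3.47 points, z = 5.46/3.47 = 1.58, p = 0.11.
- Interval: standard error √[(0.0984 × 0.9016 + 0.1530 × 0.8470)/183] = 3.45 points, so 5.46 ± 1.96 × 3.45 = -1.3 to +12.2 points.

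Table 3 as planned would print the counts and p = 0.11. It would not print the upper limit of 12.2 points.

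**6. Continuous measures.** With 172 per arm, power is 79% for a 0.3 SD difference and 96% for 0.4 SD. Low power is mainly an issue for the binary outcomes.

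**The case against.** A reader might infer that the plan will let p > 0.05 pass as proof that safety and quality are maintained. The SAP has no such rule. In section 2.7 the idea of benefit being maintained refers to long-term survival, and section 6.4.8 handles 24-month mortality with an interval against a bound. Neither 6.4.2 nor 6.4.4 sets a decision threshold, and 6.4.2 asks for caution. That caution is tied to the per protocol set, however, and 6.4.4 has none.

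A reader might also infer that relevant harms would usually be missed. That depends on event rates and on a threshold of relevance, and the SAP gives neither. The power table contradicts it for 10-point rises from 5% to 20% and for a 7-point rise from 5%.

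The calculation does not fit every outcome. The chi-square figures apply to complications and binary margin measures, not to the ordered R categories, and no test is named for early mortality. The safety set is grouped by the procedure first initiated, so its sizes might be nearer 193 v 173. That barely matters: exact power for 10% v 15% is 0.305 against 0.308.

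Finally, counts and denominators are shown, so a reader could derive an interval for a binary outcome. This is true, but the plan's main safety estimate should not be left to the reader, and per-arm Kaplan-Meier intervals do not give the difference. These outcomes are secondary and no test or dataset has to change, which limits the weight of the point without removing it.

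**Conclusion.** The point holds as a gap in planned estimation. For surgical quality, key complications and early mortality, the SAP specifies p-values (tests of equality where a test is named) and no between-arm effect with an interval, although it asks for intervals elsewhere. The first paper could then report no significant difference without showing how large an excess with LAO the data allow.

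The size rests on assumed base rates of 5% to 30% and about 183 per arm: power is 17% to 44% for a 5-point rise, and 41% or less for a 7-point rise at base rates of 15% or more. The documents do not support going further, either to a claim that the plan equates non-significance with safety or to a claim that harms in general would be missed.

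**What to change.** In sections 6.4.2 and 6.4.4 and in Tables 3 and 4, report the between-arm effect (LAO against OO) with its 95% confidence interval as the main result:

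- risk difference for each binary complication, positive margins, and 30- and 90-day mortality;
- odds ratio for Clavien-Dindo grade and for the ordered R and pStage categories;
- difference in location for node counts.

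Keep the p-value as secondary. Add a sentence such as: *A non-significant difference will not be read as equivalence; the report will state the largest excess risk with LAO compatible with the 95% confidence interval.*

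No margin is needed unless equivalence or non-inferiority is to be claimed. If it is, the margin needs clinical justification and should be fixed before unblinded results are seen. As an illustration, borrowing the 7-point mortality bound with 80% power and one-sided 2.5% would need 153 per arm at a 5% event rate but 289 at 10%, so this trial could support such a claim only for events near 5%.

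The cost is some SAP wording and one extra column in two tables, with no new data or patients. The downside is that the intervals will be wide: half-widths of about 4.5 to 9.4 points under the assumed rates. They make the uncertainty visible but do not show equal safety.
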